7.2.7. ECG and QTc Interval

Standard electrocardiogram (ECG): 12-lead (with a 10-second rhythm strip) tracing will be used for all ECGs. It is preferable that the machine used has a capacity to calculate the standard intervals automatically. At each time point (see the Schedule of Activities in the Protocol), 3 consecutive ECGs (except single ECG at screening and End of Treatment) will be performed at approximately 2 minutes apart to determine the mean QTcF interval. If the mean QTcF is prolonged ≥ 501 msec, ie, CTCAE Grade ≥ 3 , then the ECGs should be re-evaluated by a qualified person at the site for confirmation as soon as the finding is made, including verification that the machine reading is accurate.

7.3. Covariates

Not applicable.

7.4. Definition of baseline for efficacy and safety analyses

The last available assessment prior to the start of study treatment is defined as 'baseline' value or 'baseline' assessment for safety and efficacy analyses. If an assessment is planned to be performed prior to the first dose of study treatment in the protocol and the assessment is performed on the same day as the first dose of study treatment, it will be assumed that it was performed prior to study treatment administration, if assessment time point is not collected or is missing. If assessment time points are collected, the observed time point will be used to determine pre-dose on study day 1 for baseline calculation. Unscheduled assessments will be used in the determination of baseline. However, if time is missing, an unscheduled assessment on study day 1 will be considered to have been obtained after study treatment administration.

8. Handling of Missing Values

8.1. Missing Dates

In compliance with Pfizer standards, if the day of the month is missing for any date used in a calculation, the 1st of the month will be used to replace the missing date unless the calculation results in a negative time duration (eg, date of onset cannot be prior to day one date). In this case, the date resulting in 0 time duration will be used. Pfizer standards are also used if both month and day are missing (Jan 1 unless negative time duration). This excludes the pharmacokinetic, ECG, and pharmacodynamic analyses, which will only use the actual date collected or if date not available deem the data missing.

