- Progression Free Survival (PFS)** - is defined as the time from Cycle 1 Day 1 (CID1) to first documentation of disease progression or death due to any cause, whichever occurs first. Patients last known to be **1) alive** 2) on treatment or within the post-treatment follow-up period and 3) progression-free, are censored at the date of the last disease assessment that verified lack of disease progression. Patients who start new anti-cancer treatment prior to the end of post-treatment follow-up period and have adequate baseline and on-treatment objective disease assessments without evidence of progressive disease are censored at the date of the last objective disease assessment. Patients with inadequate baseline or no on-study disease assessments are censored at CID1 unless death occurred prior to the first planned assessment (in which case the death is an event). Patients with at least one on-study disease assessment who discontinue treatment without disease progression and without death within 28 days of discontinuation are censored at the date of the last objective disease assessment that verified lack of disease progression (if progression or death is within 28 days of discontinuation the progression or death is an event). Patients with documentation of progression or death after an unacceptably long interval (>16 weeks) since the previous disease assessment will be censored at the time of the previous assessment. If applicable, patients who are still ongoing at time of study termination by sponsor are censored at the date of study termination.

 $PFS \text{ (days)} = [\text{progression/death date} - \text{CID1} + \mathbf{1}]$.

If last adequate tumor assessment is within 6 months of CID1, any event of death or progression occurring after more than 18 weeks of last tumor assessment, then it qualifies for 2 missing and we censor at last adequate tumor assessment.

If last adequate tumor assessment is after 6 months and before 24 months of CID1, any event of death or progression occurring after more than 26 weeks of last tumor assessment, then it qualifies for 2 missing and we censor at last adequate tumor assessment.

If last adequate tumor assessment is after 24 months of CID1, any event of death or progression occurring after more than 4 months and 2 weeks of last tumor assessment, then it qualifies for 2 missing and we censor at last adequate tumor assessment.

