7.2.6. Adverse Events

Assessment of adverse events will include the type, incidence, severity (graded by the National Cancer Institute Common Terminology Criteria for Adverse Events [NCI CTCAE] version 4.03) timing, seriousness, and relatedness.

All AEs will be coded by system organ class (SOC) and preferred term using Medical Dictionary for Regulatory Activities (MedDRA). The severity of all AEs will be graded by the investigator using NCI CTCAE Version 4.03 whenever possible. For other AEs without specific CTC definitions, results are identified according to CTCAE "other" categories. Adverse events will be assigned to the appropriate cycle based on Day 1 of each cycle.

Treatment Emergent Adverse Events

An adverse event is considered a Treatment-Emergent Adverse Event (TEAE) if the event started during the effective duration of treatment (i.e., from the first dose of study treatment until last dose of study treatment+ 28 days or start of new anti-cancer therapy - 1 day, whichever occurs first).

Treatment Related Adverse Events

Treatment Related Adverse Events are treatment emergent adverse events with cause categorized by the investigator as related to study treatment. Events that are continuations of baseline abnormalities (signs and symptoms) are not considered treatment emergent, and hence are not considered treatment related, unless there is an increase in grade over baseline.

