- If CR determination depends on a residual lesion that decreased in size but did not disappear completely, it is recommended the residual lesion be investigated with biopsy or fine needle aspirate. If no disease is identified, objective status is CR.

- If progression determination depends on a lesion with an increase possibly due to necrosis, the lesion may be investigated with biopsy or fine needle aspirate to clarify status.

Subjective Progression

Patients requiring discontinuation of treatment without objective evidence of disease progression should not be reported as PD on tumor assessment CRFs. This should be indicated on the end of treatment CRF as off treatment due to Global Deterioration of Health Status. Every effort should be made to document objective progression even after discontinuation of treatment.

Table 4 Objective Response Status at each Evaluation

Target Lesions	Non-target Disease	New Lesions	Objective status
CR	CR	No	CR
CR	Non-CR/Non-PD	No	PR
CR	NE or Missing	No	PR
PR	Non-CR/Non-PD, NE or Missing	No	PR
SD	Non-CR/Non-PD, NE or Missing	No	Stable
NE or Missing	Non-PD	No	NE
PD	Any	Yes or No	PD
Any	PD	Yes or No	PD
Any	Any	Yes	PD

If the protocol allows enrollment of patients with only non-target disease, the following table will be used:

Table 5 Objective Response Status at each Evaluation for Patients with Non-Target Disease Only

Non-target Disease	New Lesions	Objective status
CR	No	CR
Non-CR/Non-PD	No	Non-CR/Non-PD
NE	No	NE
Unequivocal progression	Yes or No	PD
Any	Yes	PD

Best Overall Response

The best overall response (BOR) is the best response recorded from the randomization until disease progression or death due to any cause. This is derived from the sequence of objective

statuses. Objective statuses are not considered after objective progression is documented or after start of the first anticancer treatment post discontinuation of protocol treatment. BOR for each patient will be derived as one of the following categories.

- **Complete response (CR):** At least one objective status of CR documented before progression.
- **Partial response (PR):** At least one objective status of PR documented before progression.
- **Stable disease (SD):** At least one objective status of stable documented at least 8 weeks after randomization date and before progression but not qualifying as CR, PR.
- **Progressive Disease (PD):** Objective status of progression within 16 weeks of randomization, not qualifying as CR, PR or SD.

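### Partial death and new-therapy dates are set to the earliest possible day with no floor at last known alive or last study dose, so PFS can be dated too early and the adverse event window can close during dosing

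*SAP*

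**What the plan says.** SAP 8.1 (Missing Dates) applies one rule to any date that enters a calculation. If the day is missing, "the 1st of the month will be used to replace the missing date unless the calculation results in a negative time duration". If the month is missing as well, the rule is "Jan 1 unless negative time duration". The floor reads: "In this case, the date resulting in 0 time duration will be used". Its only example is an onset date set against day one. On scope, the section adds: "This excludes the pharmacokinetic, ECG, and pharmacodynamic analyses". There is no separate rule for death or for new anticancer therapy.

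These two dates are used in the following places:

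- **PFS (SAP 7.1)** runs from C1D1 "to first documentation of disease progression or death due to any cause, whichever occurs first". Death or progression within 28 days of stopping treatment counts as an event. Appendix 3 Table 6 dates a death event at the death and does not require it to follow the last scan.
- **New therapy in PFS and TTP.** SAP 7.1 addresses "Patients who start new anti-cancer treatment prior to the end of post-treatment follow-up period" and censors those without evidence of progression at the last objective assessment. Table 7 (TTP) has a matching row, also limited to patients without progression. Table 6 (PFS and DOR) has no new-therapy row.
- **BOR (SAP Appendix 2)** disregards objective statuses "after start of the first anticancer treatment post discontinuation of protocol treatment".
- **TEAE window (SAP 7.2.6)** ends at last dose plus 28 days "or start of new anti-cancer therapy - 1 day, whichever occurs first".

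**The concern.** Imputing to the earliest day is a reasonable convention for adverse event onset, because it tends to count an event as emergent. For death and new therapy it can give orders of events that cannot have happened. A patient can be recorded as dead before a scan that showed the patient alive, or as starting the next therapy before the last study dose. The negative-duration floor does not prevent the first, because PFS is measured from C1D1 and the floor acts only there. Nothing in SAP 8.1 ties an imputed date to last contact, last dose or last scan.

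At stake are the time, and sometimes the status, of deaths in PFS; the time of deaths in OS if OS is summarised; the count of TEAEs, since adverse events are a primary endpoint in both parts; and the statuses that feed BOR, since response is the primary efficacy endpoint of Part 2.

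**Working it through.** The plan gives no figure on this point to reproduce. The rules are those set out above. Arm sizes of about 40 (Arm A) and 30 (Arms B and C) come from Protocol 3.2. The share of partial dates is an assumption. The patients are hypothetical, all with C1D1 on 1 September 2021 and scans on 27 October, 22 December and 16 February (8-weekly).

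**1. Size of the shift.** Over the 730 days of 2021 and 2022, shift = true date − imputed date. Day missing: mean 14.7 days, maximum 30. Month and day missing: mean 182 days, maximum 364.

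**2. Chance of a reversed order.** For a death or therapy start k days after a scan, the share of calendar dates for which the imputed date falls before that scan:

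| k (days) | Day missing | Month and day missing |
|---|---|---|
| 7 | 0.74 | 0.98 |
| 14 | 0.51 | 0.96 |
| 21 | 0.28 | 0.94 |
| 28 | 0.05 | 0.92 |

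**3. Death on treatment.** An extra clean scan on 10 March 2022, dosing to 15 March, death 25 March. PFS = death − C1D1 + 1.
- True date: event, day 206.
- Recorded as March 2022, set to 1 March: event, day 182, before the clean scan.
- Recorded as 2022, set to 1 January: event, day 123.

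The death is an event each time, only earlier. With a floor at the day after last known alive (here at least 15 March), the date becomes 16 March, day 197.

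**4. Death after treatment.** Same scans, last dose 20 March, death 25 April.
- True date: 36 days after last dose, outside 28 days; censored at the 10 March scan, day 191.
- Set to 1 April: 12 days after last dose; event, day 213.

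A censoring has become an event. The floor corrects this only if a later contact is on record. If the patient was seen on 20 April, death becomes 21 April, 32 days after last dose, and is censored again. With no contact after 20 March, it stays at 1 April.

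**5. TEAE window.** Last dose 8 March, new therapy 25 March. Window end = the earlier of last dose + 28 days (5 April) and new therapy − 1 day.
- True date: 24 March.
- Recorded as March, set to 1 March: 28 February. Onsets from 1 to 24 March are lost, including those on dosing days 1 to 8 March.
- If the zero-duration floor is read against last dose (the SAP does not say this): new therapy 8 March, window end 7 March, so an onset on the last dosing day is still lost.
- Floor at last dose + 1 day: new therapy 9 March, window end 8 March. All dosing days are kept.

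**6. BOR.** With new therapy set to 1 March, any status later in March is ignored. With the year only, it is set to 1 January and the 16 February scan is ignored too. If that scan showed or confirmed a response, confirmed ORR changes.

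**7. PFS and TTP, conditional.** Suppose new therapy is programmed as a cut-off by date. Take the patient in step 5, with a scan showing progression (PD) on 15 March.
- True date: PD event, day 196.
- New therapy set to 1 March, or floored at last dose 8 March: censored at 16 February, day 169.
- Last dose on 15 March with the floor there: PD event kept, day 196.

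**8. Scale of step 7.** Expected flips = n × share partial × 0.507, where 0.507 is the unrounded k = 14 entry with day missing. This assumes that every patient progresses and starts therapy 14 days later, that there is no last-dose floor, and that 5% to 20% of dates lack the day.
- n = 30: 30 × 0.05 × 0.507 = 0.76 to 30 × 0.20 × 0.507 = 3.04.
- n = 40: 40 × 0.05 × 0.507 = 1.01 to 40 × 0.20 × 0.507 = 4.05.

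This is an upper-end illustration of a reading that the SAP does not state.

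**The case against.** A reader might infer that the rule turns deaths into censorings. It does not: Table 6 keeps a misplaced death as an event, and where status changes in the traces it goes from censored to event. In TTP, death is never an event.

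A reader might also infer that PD events are lost from PFS under the stated rules. The documents do not say that. Table 6 has no new-therapy row, and both SAP 7.1 and Table 7 censor only patients without progression; a patient with a PD scan has evidence of it. The instruction to disregard later statuses appears only under BOR. Under Protocol 3.1 treatment continues until progression, and Protocol 5.7.1 bars other anti-tumor treatment on study drug, so many PD scans will fall on or before the last dose.

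Nor is every partial date affected, given the three exempt analyses and the zero-duration floor. SAP 8.1 refers to company standards that are not reproduced and might treat death or therapy dates separately.

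On size, deaths that count for PFS are on treatment or within 28 days of it, when serious adverse events are actively collected and fatal ones reported immediately (Protocol 8.1). A year-only death date there is unlikely, so 364 days is a calendar maximum. Dropping a PD status from BOR leaves a non-responder a non-responder. No hypotheses are tested, and PFS and TTP are secondary.

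All of this limits the point. What stands is that the rule as written allows impossible dates for death and new therapy, and that the BOR and TEAE cut-offs are explicit.

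**Conclusion.** The point holds in a limited form. The negative-duration floor does not stop a death being dated before the patient was last known alive, or new therapy being dated before the last study dose. The first shortens PFS (and OS, if summarised) or converts a censoring into an event. The second can drop adverse events that began during dosing and can remove statuses from BOR. Conversion of a PD event into a PFS or TTP censoring is possible only if the programming applies new therapy as a cut-off by date; the SAP should settle this because Table 6 is silent.

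The shift per affected date is known: 14.7 days on average for a missing day and 182 for a missing month and day. The effect on the results is not, because it depends on the share of partial death and new-therapy dates, which the documents do not give. The change is worth making because it is cheap and removes impossible dates, not because a large bias has been shown.

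**What to change.** Add to SAP 8.1:

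- **Death:** the later of the 1st of the month (or 1 January) and the day after last known alive.
- **New anticancer therapy:** the later of the 1st of the month (or 1 January) and last study dose + 1 day.
- Keep both within the known month or year.
- **Progression and new therapy in the same partial period:** state one order, for example progression first, and report a sensitivity analysis with the other. This is needed because the last-dose floor alone does not settle it: in step 7 it gives 9 March, still before the 15 March scan, so under a date cut-off the result is day 196 with progression first and day 169 otherwise. An unconditional progression-first rule would make every ambiguous case an event, so it should not stand without the alternative.
- **AE onset:** keep the current rule.

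Add a new-therapy row to Table 6 so that PFS and DOR handling is explicit, and report how many death and new-therapy dates were partial.

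The cost is a few SAP lines, a small derivation change and one sensitivity run. Little or no new data are needed: death, last assessment and last contact dates are already to be listed (SAP 7.1), and Protocol 6.4 asks for a last-known-alive date for patients lost to follow-up. The downside is a small departure from the company default for two date types. Imputed dates will still tend to be early where no later contact is on record.

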8.2. Efficacy Analysis

Censoring rules for time-to-event endpoints are detailed in Section 11.3 [Appendix 3](#).

8.3. Pharmacokinetics

Concentrations below the limit of quantification

In all data presentations (except listings), concentrations below the limit of quantification (BLQ) will be set to zero. (In listings BLQ values will be reported as "<LLQ", where LLQ will be replaced with the value for the lower limit of quantification.).

Deviations, missing concentrations and anomalous values

Patients who experience events that may affect their PK (eg, incomplete dosing due to vomiting) may be excluded from the PK analysis.

In drug concentration summary tables and plots of median PK profiles (plots of PK profiles will only be done for Part IA and IB patients), statistics will be calculated with concentrations set to missing if one of the following cases is true:

1. A concentration has been reported as ND (ie, not done) or NS (ie, no sample),
2. A deviation in sampling time is of sufficient concern or a concentration has been flagged anomalous by the pharmacokineticist.

Note that Summary statistics will not be presented at a particular time point if more than 50% of the data are missing.

An anomalous concentration value is one that, after verification of bioanalytical validity, is grossly inconsistent with other concentration data from the same individual or from other subjects. For example, a BLQ concentration that is between quantifiable values from the same

dose is considered as anomalous. Anomalous concentration values may be excluded from PK analysis at the discretion of the PK analyst.

Pharmacokinetic parameters

Actual PK sampling times will be used in the derivation of PK parameters. If a PK parameter cannot be derived from a patient's concentration data, the parameter will be coded as NC (ie, not calculated). (Note that NC values will not be generated beyond the day that a subject discontinues).

In Summary tables, statistics will not be presented for a particular treatment group if more than 50% of the data are NC. For statistical analyses, PK parameters coded as NC will also be set to missing.

If an individual patient has a known biased estimate of a PK parameter (due for example to an unexpected event such as vomiting before all the dose is absorbed in the body), this will be footnoted in Summary tables and will not be included in the calculation of Summary statistics or statistical analyses.

QTc

For the QTc analyses, no values will be imputed for missing data.

Pharmacodynamic parameters

Missing data for the pharmacodynamic parameters will be treated as such and no imputed values will be derived.

9. STATISTICAL METHODOLOGY AND STATISTICAL ANALYSES

9.1. Statistical Methods

No formal hypothesis testing will be performed in this exploratory study.

Analyses of Time-to-Event Endpoints

Time-to-event endpoints will be summarized using the Kaplan-Meier method and displayed graphically when appropriate. Median event times and 2-sided 95% confidence intervals for each time-to-event endpoint (Brookmeyer and Crowley, 1982) will be provided.

Analyses of Binary Endpoint

The rates of binary endpoints will be provided along with the corresponding 2-sided 95% confidence intervals using an exact method.

Analyses of Continuous Data

Descriptive statistics, such as the mean, standard deviation, coefficient of variation, median, minimum, and maximum values, will be provided for continuous endpoints.

9.2. Statistical Analyses

9.2.1. Primary Analysis

Dose Limiting Toxicity (DLT) is the primary endpoint of the study, which will be summarized by dose level using the Per Protocol Analysis Set for patients in the dose escalation portion of the study. A listing of the DLTs will also be provided.

9.2.2. Secondary Analyses

9.2.2.1. Efficacy Analysis

Overall this First-in-Patient study anti-tumor activity is a primary objective for Part 2 of the study. Tumor response will be presented in the form of patient data listings that include, but are not limited to, tumor type, starting dose, tumor response at each visit, and best overall response. In addition, progression date, death date, date of first response and last tumor assessment date, and date of last contact will be listed. Objective response rate (ORR), progression-free survival (PFS), time to progression (TTP), and duration of response (DOR) will be summarized and presented. The definition of each response category is provided in [Appendix 2](#) (RECIST 1.1).

Efficacy analysis will be summarized by dose cohorts for Part 2 of the study (dose expansion). For Part 1 (dose escalation), no formal efficacy analysis will be presented; instead, results will be listed.

For response-based metrics (BOR, ORR and DOR), analyses will be presented based on confirmed responses. Analysis of progression free survival and time to progression are defined as time from the date of first dose. Summaries of the number and percentage of subjects with PFS, and TTP and data listing by tumor type and dose will be generated. If applicable, the PFS may also be summarized using the Kaplan-Meier method at all or some of the following timepoints: PFS, DOR, and TTP at 3, 6, 9, 12, 18, and then every 6 months.

The 95% confidence intervals will be generated. Confidence intervals for medians and quartiles will be based on the Brookmeyer-Crowley method. Confidence intervals for the estimated probability of an event at a particular time point will be generated using the

Greenwood formula. Duration of response will be summarized with number of responders, number and percentage of event/censorship, mean, standard deviation, minimum, maximum and median of duration in unit of months. ORR will be summarized by number of subjects meeting respective criteria, percentage. The 95% confidence intervals will be generated for PFS, TTP, and ORR. Definitions of PFS, TTP, DOR, and ORR are outlined in section 7.1 of this SAP. Supportive figures depicting the change in tumor size may also be provided.

The following table provides an overview of the efficacy analysis.

Table 3 Summary of Efficacy Analysis

Endpoint	Analysis Set	Statistical Method	Model/Covariates/Strata	Missing Data	Interpretation
Overall (confirmed) response	Full Analysis Set, Response Evaluable set.	Exact CI	By dose range/arms	Censored per Section 11.3	Secondary Analysis
Progression Free Survival (PFS)	Full Analysis Set.	Kaplan-Meier ¹	By dose range/arms.	Censored per Section 11.3	Secondary Analysis
Time to Progression (TTP)	Full Analysis Set.	Kaplan-Meier	By dose range/arms.	Censored per Section 11.3	Secondary Analysis
Duration of (confirmed) Response (DOR)	Full Analysis Set.	Kaplan-Meier	By dose range/arms.	Censored per Section 11.3	Secondary Analysis

¹ Kaplan EL, Meier P. Nonparametric estimation from incomplete observations. J Am Stat Assoc 1958; 53:457-481.

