Part IA: Single Agent Dose Escalation and Part JB: Combination Dose Finding	

 To document any preliminary evidence of anti-tumor activity of PF-06873600. 	
 Objective Response (OR), as assessed using the Response Evaluation Criteria in Solid Tumors (RECIST) version 1.1. Time-to-event endpoints: eg, Duration of Response (DOR), Progression-Free Survival (PFS), Time to Progression (ITP).

 To evaluate the pharmacodynamic (PD) markers of CDK pathway modulation following treatment with PF-06873600 in tumor. 	
 Modulation of PD biomarkers (eg, pRb, Ki67) of CDK in tumor.
CCI [REDACTED]	[REDACTED]
[REDACTED]	[REDACTED]
[REDACTED]	[REDACTED]
[REDACTED]	I [REDACTED]
[REDACTED]	I [REDACTED]

Part 2: PF-06873600 Single Agent and Combination Dose Expansion	
Primary Objective(s):	Primary Endpoint(s):

To evaluate the preliminary antitumor activity and confirm the safety and tolerability of PF-06873600:
 
In combination (at the RDE from Part 1B) in patients with:
 
 HR-positive/HER2-negative advanced or mBC {PF-06873600 + fulvestrant} (second or third line setting); HR-positive/HER2-negative advanced or mBC {PF-06873600 + a nonsteroidal aromatase inhibitor} (CDK4/6i naive); HR-positive/HER2-negative advanced or mBC {PF-06873600 + fulvestrant}- (CDK4/6i naive). 	
 Preliminary antitumor activity measure for efficacy includes OR, as assessed using RECIST 1.1. Safety and tolerability: 
 Adverse Events as characterized by type, frequency, severity (as graded by National Cancer Institute Common Terminology. Criteria for Adverse Events (NCI CTCAE v 4.03) timing, seriousness and relationship to study therapy. Lab abnormalities as characterized by type, frequency, severity (as graded by NCI CTCAE v 4.03) and timing. Vital sign abnormalities. Heart rate corrected QT interval (eg, QTcF).

Part 2: PF-06873600 Single Agent and Combination Dose Expansion	
Secondary Objective(s):	Secondary Endpoint(s):

 To farther explore preliminary antitumor activity of PF-06873600. 	
 Time-to-event endpoints: eg, DOR, PFS, overall survival (OS) and TTP.

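### SAP 9.2.2.1 lists a mean, SD and median for duration of response without saying how censored durations enter; as listed, the mean would be biased short and the median is ambiguous

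*SAP*

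**What the plan says.** SAP 2.3 places DOR among the Part 2 secondary endpoints of the time-to-event type: "Time-to-event endpoints: eg, DOR, PFS, overall survival (OS) and TTP".

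SAP 9.1 then sets one rule for each kind of endpoint:
- Time-to-event: "Time-to-event endpoints will be summarized using the Kaplan-Meier method and displayed graphically when appropriate", and "Median event times and 2-sided 95% confidence intervals for each time-to-event endpoint (Brookmeyer and Crowley, 1982) will be provided".
- Continuous: "Descriptive statistics, such as the mean, standard deviation, coefficient of variation, median, minimum, and maximum values, will be provided for continuous endpoints".

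Table 3 in SAP 9.2.2.1 follows the time-to-event rule. Its row reads "Duration of (confirmed) Response (DOR) Full Analysis Set. Kaplan-Meier", with censoring referred to Section 11.3.

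The text of 9.2.2.1 departs from this. Its sentence specific to DOR is: "Duration of response will be summarized with number of responders, number and percentage of event/censorship, mean, standard deviation, minimum, maximum and median of duration", in months. Three other statements in that text bear on DOR:
- Kaplan-Meier estimates at fixed times are optional ("If applicable, the PFS may also be summarized using the Kaplan-Meier method at all or some of the following timepoints"), although DOR is named in the list of timepoints that follows.
- Brookmeyer-Crowley is the stated interval method for medians and quartiles.
- The closing list of endpoints that receive a 95% interval names PFS, TTP and ORR, but not DOR.

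Table 6 in Appendix 3 gives the censoring rules for PFS and DOR together. Censored situations include stopping treatment for toxicity or another reason, and being ongoing when the sponsor terminates the study.

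**The concern.** The sentence borrows most of the list that 9.1 reserves for continuous data and applies it to an endpoint that the same sentence says has censored values. A mean or SD of observed times does not estimate the mean or SD of response duration once some responses are cut off by the end of follow-up. It partly measures how long patients were followed.

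A programmer who works from the DOR sentence alone would produce descriptive statistics with no interval. One who works from Table 3 would produce a Kaplan-Meier median. Both follow the SAP, and they can give different numbers under the same label. At stake is a reported DOR that is too short, or two DOR medians that do not agree, in a single-arm expansion where DOR is read alongside the response rate.

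**Working it through.** **What the SAP defines.** For the median, 9.1 supplies a censoring-adjusted definition (Kaplan-Meier, Brookmeyer-Crowley). For the mean and SD, neither 9.1, 9.2.2.1, Table 3 nor Appendix 3 supplies one; no restricted mean is mentioned. What remains is to compute them from observed times, either with censored durations counted at their censoring date or with events only.

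**Direction for the mean.** Let T be the true duration and C the follow-up after response. The observed time is min(T, C), and E[T] − E[min(T, C)] = E[max(T − C, 0)]. This is positive whenever there is any chance of censoring, whatever the distributions.

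**Direction for the median.** With C independent of T, the raw median m solves P(T > m) × P(C > m) = 0.5. If all follow-up exceeds the true median, P(C > m) = 1 at that point and the raw median is correct. If censoring begins before the true median, the raw median is short.

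**Illustrative size.** The plan states no expected DOR, censoring share or follow-up, so there is no figure of its own to reproduce. Assume T is exponential with median M, so that λ = ln 2 / M and the true mean is 1/λ, and that C is uniform on (a, b). Then:
- censored share p = (e^(−λa) − e^(−λb)) / (λ(b − a))
- raw mean = (1/λ)(1 − p)

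For M = 9, a = 2, b = 18: λ = 0.07702 and 1/λ = 12.98. So p = (0.8572 − 0.2500) / 1.2323 = 0.493, and the raw mean is 12.98 × 0.507 = 6.6 months.

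For M = 9, a = 2, b = 12: p = (0.8572 − 0.3969) / 0.7702 = 0.598, and the raw mean is 12.98 × 0.402 = 5.2 months.

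The same formulas, with the raw median from the equation above, give (months):

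| True median | Follow-up | Censored | True mean | Raw mean | Raw median |
|---|---|---|---|---|---|
| 9 | 2–18 | 49% | 13.0 | 6.6 | 5.6 |
| 9 | 3–24 | 39% | 13.0 | 7.9 | 6.6 |
| 12 | 3–24 | 49% | 17.3 | 8.9 | 7.7 |
| 18 | 3–24 | 61% | 26.0 | 10.1 | 9.1 |
| 12 | 12–24 | 36% | 17.3 | 11.1 | 12.0 |

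The last row is the case in which the raw median is right and the raw mean is still short.

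Simulation (200,000 durations per scenario) agrees. In all 20 scenarios, with true medians of 6 to 24 months and four follow-up windows, the raw mean was short. The SD is affected too: with a true median of 12 and follow-up of 3–24 months, the raw SD was 6.0 against 17.3. Using events only was shorter still, with a mean of 6.5 and a median of 5.2 in that scenario.

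**Small samples.** With 10 responders, a true median of 12 and follow-up of 3–24 months (4,000 replicates), the typical raw median was 7.7 and the typical Kaplan-Meier median 11.7. The Kaplan-Meier median was not reached in 20% of replicates.

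**The case against.** The best reply is that the SAP, read as a whole, already handles DOR correctly. DOR is classed as time-to-event, 9.1 requires Kaplan-Meier with a Brookmeyer-Crowley interval for every such endpoint, Table 3 repeats this for DOR, and the text of 9.2.2.1 names Brookmeyer-Crowley for medians and quartiles shortly before the DOR sentence. On that reading the listed median is the Kaplan-Meier median. Event and censoring counts appear in the same summary, and the patient listings carry first response, progression and last assessment dates, so a reader could see the censoring. DOR is secondary, no hypotheses are tested and no decision rule uses it.

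Most of this stands. A reader might infer from the sentence that the SAP orders censored durations to be counted as complete, that Kaplan-Meier is replaced, or that two conflicting medians will be reported. The documents do not support any of these. The SAP never says that censored times count as complete, Kaplan-Meier remains planned, and two medians are possible but not certain. Nor is a raw median short in every case.

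A reader might also infer from the early termination that most responses will be censored. The sponsor's decision is dated 07 September 2022 and the primary completion date is about 5 April 2023 (Protocol Appendix 8 and 13.2), but the documents give no accrual dates, number of responders or expected DOR. Follow-up could be short or long.

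The reply does not rescue the mean and SD. No section gives them a definition that accounts for censoring, and a censoring count beside a biased mean does not correct it.

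**Conclusion.** The point holds as an unreconciled and partly undefined summary of a secondary endpoint. The mean and SD of DOR in 9.2.2.1 have no censoring-adjusted definition and do not belong with a time-to-event endpoint under the SAP's own 9.1. If they are computed from observed times, the mean is short whenever any response is censored, and Table 6 provides for censoring. That direction needs no assumption about this trial.

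The median is ambiguous rather than wrong. The Kaplan-Meier reading is available and probably intended, but the wording also permits a raw median, which is short when censoring begins before the true median.

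The sizes, such as 6.6 against 13.0 months, are illustrative. They rest on an exponential DOR, uniform follow-up independent of duration, and assumed values for both. The change is worth making because it is almost free and prevents a misleadingly short figure. It does not affect the primary endpoints or any trial decision.

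**What to change.** In SAP 9.2.2.1:
- Delete the mean and SD of DOR, or replace them with a restricted mean whose truncation time is stated.
- State that the DOR median and quartiles are Kaplan-Meier estimates in confirmed responders, with Brookmeyer-Crowley 95% confidence intervals, and that the median is reported as not reached where that applies.
- Add DOR to the closing list of endpoints that receive a 95% confidence interval.
- Keep the number of responders and the event and censoring counts. If the minimum and maximum are kept, flag censored values.

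The cost is a few lines of SAP text and a small change to one table shell. The Kaplan-Meier output is already planned under 9.1 and Table 3, and no further data are needed.
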